Eligible VAMC patients will be randomized into one of two treatment conditions: transdiagnostic CBT or an existing evidence-based version of CBT (BAT). Both treatment conditions will include 12-16 weekly 45-60-minute individual psychotherapy sessions. The total number of sessions will vary slightly depending on participant needs and progress during therapy, as is common in most CBT approaches to psychotherapy (and will serve as a covariate in the outcome analyses). The general format of sessions will involve: 1) brief check-in; 2) review of materials from previous sessions; 3) review of homework assignments; 4) overview of new materials and insession exercises; and 5) assignment of homework for next session. Attendance and homework completion will be recorded. A full battery of self-report questionnaires and a diagnostic interview will be completed pretreatment, post-treatment, and at the 6-month follow-up to track participants' progression through treatment and maintenance. Post-treatment participant interviews will be completed at immediate post-treatment and 6-month follow-up to collect feedback on participants' perspectives on the treatments.

Table of Procedures for Each Visit – Summarized Across Treatment Conditions

Week	Content	Assessment Summary
1	Pre-Treatment Assessment	Clinical interview & self-report battery (7 measures)
2	Session 1: Psychoeducation	Brief self-report battery (3 measures)
3 4 5	Session 2: Treatment planning Session 3: Introduction to behavior therapy Session 4: Behavior therapy	Brief self-report battery (3 measures)
6	Session 5: Behavior therapy	Brief self-report battery (3 measures)
7 8	Session 6: Behavior therapy Session 7: Behavior therapy	Brief self-report battery (3 measures)
9 10 11	Session 8: Behavior therapy Session 9: Behavior therapy Session 10: Behavior therapy	Brief self-report battery (3 measures)
12 13	Session 11: Behavior therapy Session 12: Behavior therapy	Brief self-report battery (3 measures)
14	Session 13: Behavior therapy (as needed)	Brief self-report battery (3 measures)
15 16 17	Session 14: Behavior therapy (as needed) Session 15: Behavior therapy (as needed) Session 16: Relapse prevention (as needed)	Brief self-report battery (3 measures)
~18	Post-Treatment Assessment	Clinical interview, immediate treatment interview, & self-report battery (7 measures), treatment satisfaction

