~33	6-Month Follow-Up Assessment	Clinical interview, immediate treatment interview, & self-report battery (7 measures), treatment satisfaction

Note. Behavior therapy involves the introduction, teaching, in-session and between-session practice, and mastery of behavioral therapeutic techniques designed to improve symptoms of depression and anxiety, including behavioral activation (BAT group) as well as situational, physical, thought, and emotional exposures (transdiagnostic CBT group). Final treatment session will take place between sessions 12-16, as determined by provider and participants' collective decision. Final treatment session will involve relapse prevention content. Post-treatment assessment will be completed 1 week immediately after final treatment session. 6-month follow-up assessment will be completed 6-months after final treatment session.

Randomization Procedures

Participants will be randomly assigned (1:1) to one of the two study arms (*n* = 48 per arm) using a permuted block randomization procedure. Randomization will be stratified by principal diagnostic group and block size will be varied to minimize the likelihood of unmasking. After determining eligibility and completing consent and baseline assessment materials, enrolled participants will be assigned to treatment groups by the Project Research Assistant using a computer generated randomization scheme. Once a participant is randomized and attends the first session, they will be included in the intent-to-treat analysis. Randomization will occur at the participant level. As such, we will take the following steps to minimize contamination between the two arms of the study: 1) only one member of a household will be eligible for enrollment; and 2) other VAMC providers will be informed of their patients' participation in the study, but will be blinded to the treatment condition of their patients.

Transdiagnostic CBT Treatment Condition

As noted above in the Preliminary Studies section, a transdiagnostic CBT protocol was developed and revised through two demonstration studies and one focus group. The resulting protocol involves several primary components, including psychoeducation on the symptoms of depression and anxiety (session 1), assessment of motivation and setup of treatment plans (session 2), exposure therapy (sessions 3-15), and relapse prevention (final session). In addition to these primary components, optional modules are included to supplement exposure

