The full intent to treat (ITT) analysis set will comprise all randomized participants. Missing data in the full analysis set will occur if participants drop out prior to the end of the study. Participants will not be discontinued from the study because of non-adherence and all will remain in the study unless consent is withdrawn or if there are concerns regarding participant safety. Missing data for the ITT analysis set will be imputed using multiple imputation methods. The results of analyses using study completers and protocol adherers (completer and perprotocol analyses) will be compared with results using the ITT analysis set to test sensitivity of study conclusions to study drop-outs and protocol non-adherence. In addition, the information on dropout proportion will be used as one of the outcome measures of intervention feasibility.

Efficacy (Symptomatology & Quality of Life) Measures Analyses (Primary Aim 1)

The continuous measures of intervention efficacy and quality of life are APPQ, DASS, IIRS, MASA, PCL, STICSA, and V/SF-36. The primary outcome time point is at the end of the active intervention phase (immediate post-treatment) and the secondary time point is at the end of the naturalistic 6-month follow-up period. The difference in mean change from baseline to end-of-active intervention (effect sizes) for transdiagnostic CBT versus BAT control condition will be estimated via 95% CI. For the secondary time-point analyses, transdiagnostic CBT versus BAT control differences in change from immediate end-of-intervention to the 6-month follow-up will also be estimated using 95% CI. By assessing the magnitude of the between-intervention-group differences, as described by the CI, clinicians can judge whether the novel intervention provides sufficient improvement in these outcomes to suggest a clinically significant result that warrants further investigation.

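### The visit table places the 6-month follow-up at about week 33, some 10 weeks earlier than the note beneath it and the rest of the protocol imply

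*Combined protocol and SAP*

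**What the plan says.** The Table of Procedures for Each Visit (section D, Procedures) has a week column. Sessions 11 and 12 sit in weeks 12 and 13: "12 13 Session 11: Behavior therapy Session 12: Behavior therapy". Sessions 14 to 16 sit in weeks 15 to 17: "15 16 17 Session 14: Behavior therapy (as needed) Session 15: Behavior therapy (as needed) Session 16: Relapse prevention (as needed". The "Post-Treatment Assessment" follows at about week 18, and the last row, marked approximate, reads "33 6-Month Follow-Up Assessment".

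The note under the table lets treatment length vary: "Final treatment session will take place between sessions 12-16, as determined by provider and participants' collective decision". It places the post-treatment assessment one week after the final session and gives the follow-up rule: "6-month follow-up assessment will be completed 6-months after final treatment session".

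The analysis plan (section D, Efficacy Measures Analyses, Primary Aim 1) uses no week number. It says that "the secondary time point is at the end of the naturalistic 6-month follow-up period", and the analysis there is of change from the end of the intervention to that visit. Primary Aim 1 in section A, the Objective in section D and the inclusion criteria in section E.1.a also say 6 months.

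**The concern.** The row's label and the note under it say six months, but the week beside the label does not. The table is the protocol's only visit-by-visit schedule, and the row concerns the designated secondary time point, so this is more than a slip in background text.

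The stake is conditional on use. If a visit were booked from the week column, maintenance would be measured at about four months and reported as six. Durability of a treatment effect depends on time since treatment, so that result would not mean what its label says. A fixed week 33 would also make follow-up shorter for participants who had more sessions, and the number of sessions is a planned covariate in the outcome model.

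**Working it through.** **Inputs** (all from the visit table and its note)

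- Pre-treatment assessment: week 1. Session 1: week 2. Session k: week k + 1.
- Final session: session 12 (week 13) at the earliest, session 16 (week 17) at the latest.
- Post-treatment assessment: one week after the final session; table figure about 18.
- Follow-up: six months after the final session; table figure about 33.

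**Assumption.** Six months is 26 weeks (365.25 / 12 / 7 = 4.348 weeks per month, so 6 × 4.348 = 26.1). As the most lenient case I also take 24 weeks, that is, six 4-week months.

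**Step 1: which course does the table follow?** 17 + 1 = 18 reproduces the post-treatment row exactly for 16 sessions. Twelve sessions would give 13 + 1 = 14. The table therefore follows the 16-session course.

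**Step 2: can week 33 be reproduced?** Follow-up week = anchor week + six months.

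| Anchor | Anchor week | + 24 weeks | + 26 weeks |
|---|---|---|---|
| Pre-treatment assessment | 1 | 25 | 27 |
| Session 1 | 2 | 26 | 28 |
| Final session, 12 sessions | 13 | 37 | 39 |
| Post-treatment, 12 sessions | 14 | 38 | 40 |
| Final session, 16 sessions | 17 | 41 | 43 |
| Post-treatment, 16 sessions | 18 | 42 | 44 |

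No row gives 33. Working backwards, the anchor would have to be week 33 − 26 = 7, or 33 − 24 = 9 with 4-week months. Both fall in mid-treatment.

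**Step 3: what interval does week 33 imply?**

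- From the final session, 16 sessions: 33 − 17 = 16 weeks; 16 / 4.348 = 3.7 months.
- From the post-treatment visit, 16 sessions: 33 − 18 = 15 weeks; 15 / 4.348 = 3.4 months.
- From the final session, if week 33 is held for 12 sessions: 33 − 13 = 20 weeks; 20 / 4.348 = 4.6 months.

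**Step 4: size of the discrepancy against the note**

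- 16 sessions: 43 − 33 = 10 weeks, and 10 / 26 = 38% of the interval (8 weeks with 4-week months).
- 12 sessions, week 33 held: 39 − 33 = 6 weeks, and 6 / 26 = 23% (4 weeks with 4-week months).

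**Step 5: effect on the interval analysed.** The secondary analysis concerns change from post-treatment to follow-up. Under the note that interval is 26 − 1 = 25 weeks. Under the table it is 15 weeks, which is (25 − 15) / 25 = 40% shorter.

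**The case against.** The strongest reply is that this is one approximate number, out of line even with its own row label. The operative rule stands directly beneath the table and is tied to each participant's final session. Because treatment can end at any session from 12 to 16, no single week could be the booking rule. The table is headed as a summary across conditions, and no section says that staff schedule from it. The Project Timeline also leaves room for a full six months: recruitment and active treatment end at month 45 and the trial at month 54, nine months later.

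Most of this stands, and it limits the point. A reader might infer that the plan holds two competing definitions of the secondary time point. The documents do not support that: the narrative text says six months throughout, and the analysis plan never refers to a week. A reader might also infer that all 96 participants would be followed up early, or that follow-up lengths would be mixed. Either would require visits to be booked from this cell, which nothing in the documents establishes.

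The reply does not rescue the figure. The approximation sign cannot cover 6 to 10 weeks when the adjacent approximate figure, week 18, is exact for 16 sessions. The cell reads cleanly and in order after the post-treatment row, so damage in text extraction is an unlikely explanation.

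**Conclusion.** The week figure for the follow-up visit is wrong as written against the note beneath it. On the 16-session course that the table follows, it is about 10 weeks early: 16 weeks after the final session, where the note implies 26. For a 12-session course with week 33 held, it is 6 weeks early. This rests on the table's own week numbering and on six months being about 26 weeks; with 4-week months the figure is still 4 to 8 weeks early.

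It is most likely a clerical error in one cell. The definition of the secondary time point in the text is sound, and harm to the follow-up analysis arises only for visits actually booked from the table. The primary time point (immediate post-treatment), the sample size and alpha do not depend on it. It is worth correcting because the cell belongs to the only visit-by-visit schedule and the correction costs almost nothing.

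**What to change.** Reconcile the last row of the visit table with its note so that both give the same time, and express the row relative to each participant's final session instead of as one fixed study week. Under the note's rule the cell would read about week 39 (12 sessions) to week 43 (16 sessions).

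The cost is one cell. No visits or participants are added. Recording the actual number of days from the final session to the follow-up visit would be a sensible low-cost addition, since it would let the analysis show the interval achieved, but the error does not require it.

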The full battery of self-report questionnaires and a diagnostic interview will be completed pre-treatment, immediate post-treatment, and at the 6-month follow-up to track participants' progression through treatment and maintenance. These time points for the assessments are consistent with CBT research with Veterans with depressive/anxiety disorders. To reduce the likelihood of missing data, all assessments will be scheduled separately from normal treatment sessions (intake appointment, one week following the final treatment session, and at 6-month follow-up). Additional staff training will be required prior to administration of the diagnostic interview. All assessments will be completed by the Project Research Assistant. All assessment staff will be required to observe the Principal Investigator administer the test twice and then administer the test twice themselves under the direct observation of the PI. All assessment staff will be blinded to treatment condition and supervised by the Principal Investigator. Assessments will be recorded to investigate inter-rater reliability. In addition to the pre- and post-treatment and follow-up assessments with the full battery, a brief assessment involving a few self-report measures (e.g., Depression Anxiety Stress Scales, Illness Intrusiveness Rating Scale, and State-Trait Inventory for Cognitive and Somatic Anxiety) will be completed biweekly to monitor symptoms during the course of treatment.

Albany Panic and Phobia Questionnaire (APPQ). The APPQ is a 27-item self-report measure that assesses agoraphobia, social anxiety, and interoceptive avoidance. Each subscale has been shown to have good internal consistency (α s > .85) and temporal stability (rs > .87).

Anxiety Disorder Interview Schedule-5 (ADIS-5). The ADIS-5 is a well-established, semi-structured interview designed to assess a wide range of Axis I disorders. The ADIS-5 assesses current and past diagnoses with DSM

diagnostic criteria, severity scores, and lists of feared and avoided situations for the anxiety disorders. The ADIS has demonstrated excellent inter-rater reliability and validity of depressive/anxiety disorder diagnoses.

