It is essential that the transdiagnostic CBT is agreeable to VAMC patients. Thus, structured interviews will be completed with participants at post-treatment and 6-month follow-up to evaluate the presentation, format, and active components of the treatment. The two time points will assess participants immediate (post-treatment) and

delayed (6-month follow-up) reactions to treatment. The interview methodology allows for the acquisition of data through open discussion of predetermined topics as facilitated by the interviewer. Interviews will be conducted by the Project Research Assistant and will follow pre-determined areas of discussion. The discussion will use openended questions, including follow-up probes and examples. These 30-60 minute interviews will be completed with all participants that completed the treatment in the transdiagnostic CBT condition. Interviews will be audio recorded for transcription and interviewers also will keep notes on the discussion.

The following are elicitation questions that will be discussed in the interviews:

- 1. What did you think about the treatment? What do you like about it? What don't you like?
- 2. What aspects of the treatment did you find to be most helpful and why?
- 3. Would you recommend this treatment to other Veterans with similar problems with anxiety/depression? If so (or if not), why?
- 4. Are there any additional things that should be included in the treatment that were not discussed?

At the completion of the interviews, all audio recordings and facilitator notes will be transcribed by the project staff. The overarching goal of the analysis of these data is to identify a set of thematic categories and to assign these categories to higher-order categories to provide a clear picture of the data. Multiple steps will be involved in the analysis of the data:

- 1. *Narrative descriptions.* Specific sections and quotes from the narratives will be carefully selected as exemplars of the content to characterize the general feel of the data.
- 2. Content analysis. This step involves the identification of relevant examples, themes, and patterns in the data. The data will be organized and reviewed by the project team to first develop thematic categories for the relevant quotes and then eventually come to consensus about the themes. The content analysis is based the expectation that important insights will emerge through the evaluation from several different perspectives.

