All participants will randomized into either a transdiagnostic CBT psychosocial treatment for the depressive/anxiety disorders or the comparison evidence-based CBT, Behavioral Activation Treatment (BAT), control condition. The transdiagnostic CBT is a variation of pre-existing psychosocial treatments that are regularly administered at the VAMC and will involved 12-16 weekly 45-60-minute individual therapy appointments. The protocol for the BAT condition will be consistent with approaches that have been shown to be effective in the past literature. Throughout the course of treatment, a multi-method assessment of psychosocial factors and quality of life will be completed for all participants, involving 1) treatment credibility and satisfaction, 2) treatment retention and adherence, 3) clinical symptomatology including anxiety, depression, and impairment, and 4) general feedback on treatment process. Participants will be paid \$10 for completing the self-report questionnaires and an additional \$10 for the completion of the ADIS-5 for a possible combined total of \$60. In addition to the pre-treatment, immediate post-treatment, and 6-month follow-up assessments with the full battery, a brief assessment involving a few self-report measures (e.g., DASS, IIRS, & STICSA) will be completed biweekly to monitor symptoms during the course of treatment.

- 1. *Demographic Information*: Age, race, sex, education, employment, and combat experience will be collected via a study specific demographic form.
- Albany Panic and Phobia Questionnaire. The APPQ is a 27-item self-report measure that assesses agoraphobia, social anxiety, and interoceptive avoidance. Each subscale has been shown to have good internal consistency (*α*s > .85) and temporal stability (*r*s > .87).
- 3. Anxiety Disorder Interview Schedule-5. The ADIS-5 is a well-established, semi-structured interview designed to assess a wide range of Axis I disorders. The ADIS-5 assesses current and past diagnoses with DSM diagnostic criteria, severity scores, and lists of feared and avoided situations for the anxiety disorders. The ADIS has demonstrated excellent inter-rater reliability and validity of depressive/anxiety disorder diagnoses. The ADIS-5 is currently in press and so an editor's copy provided in the appendix (with editor's comments). The PHI (e.g., name, address, contact information, DOB) on the demographics cover page (page 1) will be removed in the study copy.

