2. ADEQUACY OF PROTECTION AGAINST RISKS

a. Recruitment and Informed Consent

VAMC patients will be recruited from within the Primary Care Mental Health Integration psychotherapy program and CBT Clinic at the RHJ VAMC. All eligible and willing VAMC patients will be required to meet with project staff to review the purpose of the study and review the consent documentation. VAMC patients will be given ample time to discuss the study and ask questions regarding the procedures. Upon thorough review of all documentation, VAMC patients will sign the informed consent document prior to participation in study procedures.

- b. Protection against Risk
- 1. Participants will be made aware of the potential risks and benefits associated with participation and their right to withdraw from the study at any point without any negative impact on their care within the VAMC. Any participants expressing interest in withdrawing from the study will be referred for treatment within the VAMC.
- 2. Participants who appear unable to tolerate the assessment process will be offered a referral to the VAMC and terminated from the study procedures.
- As a member of the mental health service at the VAMC, the Principal Investigator will maintain active collaborations and communications with other VAMC providers to ensure appropriate continuity of care and safeguard against any adverse events.
- 4. All assessors and treatment providers will be trained and supervised by the Principal Investigator, who is a licensed psychologist. At intake, participants identified by clinical interview with both suicidal ideation and acute intent will be excluded from the study and immediately offered emergency psychiatric care at the VAMC. During the duration of the study, the Principal Investigator immediately will contact the participant and assess suicide risk when any instance of suicide risk is identified. If suicidal ideation is present but not intent, the participant will be retained in the study and reassessed for suicide risk by the investigators in one week. In cases of acute suicidal intent, state law requires immediate hospitalization and these guidelines will be followed.

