The Mental Health Service Line (MHS) is charged with all aspects of clinical care, education, and research within mental health. [name] is a Staff Psychologist within the MHS with dedicated office space, support staff, and infrastructure. [name] also will have available the full range of resources associated with the MHS and associated programs. The resources of the MHS will be available to the [name] throughout the duration of the project. The MHS also includes the CBT Clinic and Primary Care – Mental Health Integration program, both of which [name] coordinates, that provide psychosocial and psychopharmacological treatments to over 300 Veterans with depressive and anxiety disorders each year. The Research Service at the RHJ VAMC is broadbased and has approximately 250 active research protocols being conducted by over 90 investigators. The Research Service is well integrated with clinical services at RHJ VAMC and coordinates research activities closely with MUSC. Additionally, the Charleston VA Office of Research, under ACOS, [name], provides administrative support, including financial administration of projects, assistance with project budgets, advertising for and hiring new personnel, coordinating IPAs for MUSC employees, and ordering supplies.

I. INVESTIGATOR BROCHURE

n/a

J. APPENDIX

Each of the proposed self-report measures of psychiatric symptomatology were included below. The clinician rated structured clinical interviews will be uploaded separated due to an alternative file format (pdf).

Demographic Intake Questionnaire

Participant#: _____

Current Age: _____

For each of the questions below, please circle the answer that applies to you.

- 1. What is your racial or ethnic background?
 - 1 White/Caucasian
 - 2 Black/African American
 - 3 Asian American
 - 4 Hispanic
 - 5 Native American
 - 6 Other (Please list):
- 2. What is your sex/gender?
 - 1 Male
 - 2 Female
- 3. What is your relationship status?
 - 1 Single (never married)
 - 2 Single (previously married separated, divorced, or widowed)
 - 3 Married
- 4. What is your work status?
 - 1 Unemployed/looking for work
 - 2 Unemployed/retired (not actively looking for work)
 - 3 Unemployed/disability (not actively looking for work)
 - 4 Employed (part-time)
 - 5 Employed (full-time)
- 5. What is your education history (highest level achieved)?
 - 1 Did not graduate high school
 - 2 High school diploma
 - 3 Some college or 2-year college degree
 - 4 4-year college degree

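### One role both assigns the arms and completes every assessment, so the stated assessor blinding is not delivered for the post-baseline ADIS-5

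*Combined protocol and SAP*

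**What the plan says.** All references are to the combined protocol and SAP.

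- **Assignment** (section D, Randomization Procedures). Once eligibility, consent and baseline are complete, "enrolled participants will be assigned to treatment groups by the Project Research Assistant using a computer generated randomization scheme". Randomization is stratified by principal diagnostic group, with blocks of varying size.
- **Assessment** (section D, Assessment of Mental Health Symptoms, Quality of Life, and Treatment Satisfaction). "All assessments will be completed by the Project Research Assistant". Shortly afterwards: "All assessment staff will be blinded to treatment condition". Assessments are recorded so that agreement between raters can be examined.
- **Feedback interviews** (section D, Post-treatment Participant Interviews). "Interviews will be conducted by the Project Research Assistant", at post-treatment and at 6 months. This section limits them to participants who complete transdiagnostic CBT.
- **The ADIS-5** (section E.1, Sources of Materials). "The ADIS-5 assesses current and past diagnoses with DSM diagnostic criteria, severity scores". The Appendix treats the diagnostic interviews as rated by a clinician: "The clinician rated structured clinical interviews will be uploaded separated". The inclusion criteria in section E.1 make the pre-treatment ADIS-5 the basis of the qualifying diagnosis.
- **Supervision** (section E.2, Protection against Risk). "All assessors and treatment providers will be trained and supervised by the Principal Investigator".
- **Data entry** (section D, Data Entry and Management). The research assistant enters all data.

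**The concern.** A person who assigns an arm knows it. If the same role then conducts the diagnostic interview after treatment, the ratings are made with that knowledge, and a report that repeats the plan's blinding statement would claim a protection that the procedures do not provide. The ADIS-5 diagnoses and severity scores are the ratings most exposed. They bear on the aim of reducing comorbidity (section D, Objective) and on the reference in Hypothesis 1 to principal and comorbid diagnoses.

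The same arrangement raises a second question. The role that makes the baseline diagnosis, and so settles eligibility and stratum, also operates the assignment scheme. If a coming assignment could be seen or guessed, it could influence who is enrolled, and that would reach every outcome, self-report scales included.

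**Working it through.** There is no plan figure to reproduce. The check sets the provisions side by side and then counts what is exposed.

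**Step 1. Can the statements hold together?**

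| Duty | Who | Knows the arm? |
|---|---|---|
| Assigns participants | Project Research Assistant | Yes, by doing it |
| Completes all assessments | Project Research Assistant | Stated to be blinded |
| Conducts feedback interviews | Project Research Assistant | Yes, if only CBT completers are interviewed |
| Enters all data | Research assistant | Yes, if arm-revealing records are entered |

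The first two rows conflict for one role. No section splits the duties between people within it.

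**Step 2. Which ADIS-5 interviews follow assignment?** Sources of Materials pays $10 for questionnaires and another $10 "for the completion of the ADIS-5 for a possible combined total of" $60. So $60 / ($10 + $10) = 3 time points. The pre-treatment interview precedes assignment, which leaves 2.

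- Planned: 96 × 3 = 288.
- After assignment: 96 × 2 = 192.

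The 192 is a ceiling that assumes full attendance. Attendance at the later assessments is not stated, so no lower bound follows.

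**Step 3. The second route.** If only CBT completers are interviewed, being interviewed reveals CBT, and a completer who is not interviewed points to BAT. I count this only for the 6-month ADIS-5, because the order of interview and ADIS-5 within the post-treatment visit is not given. Assuming exactly 72 completers (the recruitment target, which is a minimum), it reaches up to 72 of 96 possible 6-month interviews and misses 96 − 72 = 24. These lie within the 192 and do not add to it. If both arms are interviewed, the fact of an interview reveals nothing. Its content might, but that cannot be counted.

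**Step 4. What do the planned analyses use?** The efficacy measures are APPQ, DASS, IIRS, MASA, PCL, STICSA and V/SF-36. All are self-report, so 0 of 7 are clinician-rated. No part of the Analysis Plan specifies an ADIS-5 analysis. The number of comorbidities appears there only as a possible covariate.

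**Step 5. Is the coming assignment protected?** Varied block size is the only stated safeguard. It makes the sequence harder to guess but does nothing about a scheme held by the person who assigns. Block sizes are not given, so predictability cannot be calculated.

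**The case against.** The strongest reply is that the plan speaks of assessment staff and assessors in the plural, so a second, blinded assessor may be intended. That is possible, and for this reason the text does not show what any individual rater would know. It does not resolve the conflict, because every assessment is still given to the assigning role. The recordings would also allow re-rating by someone unaware of the arm, but they are planned for inter-rater reliability and no blinded re-rating is described.

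It can also be said that little depends on this in a trial that calls itself preliminary, with self-report efficacy scales and no ADIS-5 analysis. That stands, and it limits the weight of the point.

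A reader might infer one of four things that the documents do not support:

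- **That every later ADIS-5 rating will in fact be unblinded.** The documents contradict themselves about the role; they do not establish what each rater knows.
- **That the planned efficacy estimates are biased by the rater.** No planned estimate rests directly on these ratings.
- **That selection bias occurs.** The documents fail to exclude it, which is less than showing it.
- **That the matter is confined to the post-baseline ADIS-5.** The same role also settles eligibility and stratum, operates the scheme, conducts the feedback interviews and enters the data. The MINI is another diagnostic interview, listed without a visit.

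**Conclusion.** The contradiction is certain on the text. The stated blinding is not delivered for the role that rates the post-treatment and 6-month ADIS-5, two of three planned time points and at most 192 of 288 interviews. The feedback interviews add a second route before the 6-month rating for up to 72 participants, assuming 72 completers and interviews in the CBT arm only. Direct rater bias falls mainly on the clinician-rated diagnostic interviews; its size cannot be derived from the documents. Selection bias through the assignment scheme is not excluded and not shown. The plan should be changed because it claims a protection that it does not provide and the remedy is cheap, but the point does not undermine the seven planned efficacy comparisons through rater scoring.

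Which arms are interviewed is a separate inconsistency. The interview section limits the interviews to CBT completers, Hypothesis 2 compares feedback with BAT, and the visit table lists the interview for both conditions. It adds no weight here.

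**What to change.** 1. Have existing staff outside assessment hold the computer-generated scheme and release each assignment to the project therapist, only after the Research Assistant has recorded eligibility, stratum and baseline. This also closes the concealment gap.
2. Keep arm, and any record that reveals it, out of the Research Assistant's data entry until that participant's 6-month ADIS-5 is complete.
3. Have the feedback interviews done by existing staff other than the ADIS-5 assessor. If that is not possible, hold each one after that visit's ADIS-5 and state that the 6-month ADIS-5 may be unblinded.
4. If the roles cannot be separated with existing staff, withdraw the blinding statement and report post-baseline ADIS-5 results as unblinded.

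**Cost.** A small shift of duties, some deferred data entry, and text edits to the randomization, assessment, data entry and interview sections. Participants face no added procedure. Moving the interviews, at 30 to 60 minutes each and two time points, shifts these hours:

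- CBT completers only (72 / 2 = 36, assuming an even split): 36 × 2 = 72 interviews, 36 to 72 hours.
- Completers in both arms: 72 × 2 = 144 interviews, 72 to 144 hours.
- All 96 participants: 96 × 2 = 192 interviews, 96 to 192 hours.

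The documents do not show whether existing staff have that time. Reordering the visit or withdrawing the statement avoids those hours. Separately, the sections on which arms are interviewed should be reconciled.
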